Postoperative anaemia has multiple causes. It is probably aggravated by rehydration upon admission of patients with fractures (7). There is blood loss associated with the fracture and the formation of a haematoma prior to surgery (8), but also some postoperative occult bleeding: in 546 patients with a fracture of the upper end of the femur, Foss et al. showed that post-operative occult bleeding ranged from 547 to 1473 mL, in addition to the blood loss observed during surgery. Finally, there is a degree of acute inflammatory anaemia secondary to surgery. This inflammatory component is caused by a decrease in progenitor proliferation, a reduced red blood cell half-life and iron retention by macrophages. This retention is mediated by ferritin, which is then increased, and by hepcidin, a recently discovered protein that regulates iron metabolism (9).

Loss of independence, defined as a decrease in the ability to care for oneself, is also significant after a fracture of the upper end of the femur. Of 390 patients over the age of 65 who underwent surgery for an FESF and were analysed by Vochteloos team, nearly half did not regain their previous independence after one year. Only 25% of patients who were mobile without assistance regained their previous independence within three months of surgery. Nineteen percent of patients became bedridden. The most significant risk factors were a low level of previous independence and the occurrence of postoperative confusion (10).

The consequences of a loss of independence in elderly people are manifold (11). It leads to the intervention of outside help for activities of daily living, a change of living arrangements, a change in family relationships, and a risk of abuse by carers. The economic consequences are also significant:

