2.1.2. Primary evaluation criterion

- Haemoglobin level on day 5 post-operatively (considered the post-operative haemoglobin reference level in this study)
 - In the case of patients who received a transfusion postoperatively, the reference haemoglobin level will be the haemoglobin level at the end of hospitalisation
- Change in the Activities of Daily Living (ADL) score pre-fracture and 6 months post-operatively.
A loss of independence will be defined as a decrease of one point or more in the ADL.

The reference value for haemoglobin levels was arbitrarily set at 5 days post-operatively. This is because haemoglobin levels recorded in A&E or on admission to the ward prior to surgery, or immediately post-operatively, may be influenced by factors other than isolated anaemia. Dehydration, present in the emergency department or on admission to the ward before the operation, corrected preoperatively, and postoperative haemodilution due to fluid replacement, cause the haemoglobin level to vary without there being any real deglobulation. We therefore postulate that the haemoglobin level on the 5th postoperative day can serve as a reference.

Confounding factors collected

All confounding factors related to loss of autonomy will be collected:

- Transfusion and number of red blood cell concentrates received

The indication for transfusion is at the discretion of the prescriber. However, it is generally accepted to transfuse patients with haemoglobin levels below 8 g/dL, or below 10 g/dL in cases of ischaemic heart disease or poor clinical tolerance.

- Age
- Gender
- Height, weight, Body Mass Index (BMI) calculation
- Screening for past or present higher brain function disorders
- Screening for major sensory disorders
- Screening for depressive symptoms: Mini Geriatric Depression Scale (MiniGDS)
- Comorbidities assessed using the Cumulative Illness Rating Scale - Geriatrics (CIRS-G)
- ASA score
- Number of medications (per class) taken by the patient (anticoagulants, antiplatelet agents, NSAIDs, anti-osteoporotic drugs, analgesics)

- Lifestyle and living environment
- Severe fractures before and after inclusion
- Other falls during the year
- Protein-energy malnutrition
- Iron deficiency (ferritin < 30 µg/L or CRP > 20 mg/L associated with a transferrin saturation coefficient < 15%)
- Recurrence of falls at 1, 3 and 6 months post-op

2.2. *SECONDARY OBJECTIVES AND EVALUATION CRITERIA*

2.2.1. *Secondary objectives*

The secondary objectives are to analyse:

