4. STUDY DESIGN AND PROCEDURE

4.1. STUDY SCHEDULE

The inclusion period will be 42 months. Follow-up is 6 months post-operative.

Patients may be included up to 48 hours after their arrival in the orthopaedic/orthopaedic surgery department.

a. D0 - Arrival in the orthopaedic/orthopaedic surgery department (after surgery)

Provision of the information leaflet and collection of non-objection after a reflection period.

Completion of the ASA score (*investigator*)

Biological tests (complete blood count (CBC), CRP, ferritin, transferrin saturation coefficient, albumin, vitamins B12, folate and vitamin D) (*investigator – performed on arrival at A&E or on admission to the department before surgery*)

Record of severe fractures prior to inclusion: upper end of the femur or humerus, proximal tibia, distal femur, 3 simultaneous ribs, wrist, pelvis and spine (Grio 2011 recommendations) (*investigator*)

Screening for previous or current upper function disorders (*investigator*)

Screening for major sensory disorders (*investigator*)

Completion of ADL and IADL questionnaires: **information relating to the week preceding the intervention** (*investigator: interview with patient, family or staff of residential care homes for elderly dependents (EHPAD)*)

Completion of the CIRS-G score (*investigator*)

Completion of the CAS questionnaire

Recording of lifestyle and living environment (*investigator*)

Number of medications (by class) taken by the patient on admission (anticoagulants, antiplatelet agents, NSAIDs, anti-osteoporotics, analgesics) (*investigator*) Completion of the MiniGDS score (*investigator*)

Collection of data on the procedure: time to surgery, type of fracture, surgical procedure, type of anaesthesia, weight-bearing authorisation, transfusion, number of red blood cell units received Haemoglobin measurement (if different from that taken in the emergency department or on admission to the ward before the procedure)

b. During the hospital stay: (trained orthopaedic nurses)

CAS score performed on days 1 to 3 post-operative, as well as on day 5 (or on discharge if this occurs before day 5)

Daily screening for confusion (CAM) until D10 if the patient is still hospitalised Completion of ADL questionnaires (*patient, family or nursing home resident interview*) on D5 post-operative (or on discharge if this occurs before D5)

Measurement of grip strength – Hand Grip on day 5 (or upon discharge if this occurs before day 5)

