- Screening for previous and current **higher function disorders** by interviewing family and friends or consulting the patient's file (*in-hospital – inclusion and during hospitalisation*).

- Screening for **major sensory disorders (in-hospital – inclusion)**.

- **Number of medications** (by class) taken by the patient at inclusion and at the end of hospitalisation, including anticoagulant therapy, antiplatelet therapy, NSAIDs, anti-osteoporotic therapy, analgesics, and at 6 months post-operatively, including anti-osteoporotic and analgesic therapy.

- Patient's **living arrangements (in hospital – inclusion and at 1, 3 and 6 months)**: alone, with family or partner, widowed, in a care home. Home help for shopping, cleaning and personal care.

- **Patient discharge arrangements (in-hospital – end of hospitalisation)**: return home, return to care facility, transfer to follow-up care unit.

- **Previous osteoporotic fractures (in-hospital – inclusion)**: low-energy fractures of the hip, wrist, vertebral body or humerus.

- **Albumin** level (*assessment upon admission, coupled with CRP*): a level below 35g/L upon admission indicates protein-energy malnutrition.

- **Recurrence of falls or fractures** at 1 month, 3 months and 6 months post-operatively (*telephone call*).

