5.2.1. Description of methods planned planned, including the schedule for planned interim analyses

All variables collected will be described by minimum, maximum, quartiles, mean and standard deviation for quantitative variables and by number and percentage of each modality for qualitative variables.

Analysis of the primary endpoint:

The relationship between loss of independence at 6 months and post-operative anaemia will be analysed using a logistic model. If a link is found, a multivariate analysis will be performed to confirm the independence of the anaemia/independence relationship. To do this, all potential confounding factors will be tested in a univariate analysis. Factors associated with a p value <0.20 will be retained in the multivariate model.

Analysis of secondary criteria:

- The analysis of the relationship between loss of autonomy on day 5 (or on discharge from hospital if discharged before day 5), at 1 and 3 months, and post-operative anaemia will be performed using the same method as for the primary endpoint.
- The 6-month mortality rate will be estimated with its 95% confidence interval using the Kaplan-Meier method.

The association between anaemia and mortality at 6 months will be studied using a Cox proportional hazards model in order to take confounding factors into account.

- The progression of post-operative anaemia (D0 to D15) will be described graphically.

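### Malnutrition is defined only by an albumin cut at 35 g/L and admission CRP is not a candidate confounder in its own right; list both as continuous variables

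*Combined protocol and SAP*

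**What the plan says.** Section 2.1.2 lists 16 items as confounders. One is "Protein-energy malnutrition", with no scale or coding. The only definition is in section 4.3.e, where albumin is described as an "assessment upon admission, coupled with CRP" and "a level below 35g/L upon admission indicates protein-energy malnutrition".

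Both values come from the admission panel in section 4.1.a: "Biological tests (complete blood count (CBC), CRP, ferritin, transferrin saturation coefficient, albumin, vitamins B12, folate and vitamin D". That panel is taken on arrival in the emergency department or on the ward before the operation.

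CRP is not a separate item in the list. It appears only within "Iron deficiency (ferritin < 30 µg/L or CRP > 20 mg/L associated with a transferrin saturation coefficient < 15" per cent). BMI is a separate item: "Height, weight, Body Mass Index (BMI) calculation".

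Section 5.2.1 fits a logistic model for loss of independence at 6 months. If a crude link with anaemia is found, "all potential confounding factors will be tested in a univariate analysis", and those with p below 0.20 go into the multivariate model. How each factor is coded is not stated.

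**The concern.** The multivariate model is meant to show that the haemoglobin association is independent of other factors. Undernourished or inflamed patients may plausibly have both lower haemoglobin and worse recovery. Any part of that shared variation which the covariates do not remove is credited to anaemia.

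Two features of the list weaken the adjustment.

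- Read literally, malnutrition is a yes/no variable. Patients with albumin of 34 and 22 g/L would then be treated alike.
- Inflammation has no term of its own. Through the iron-deficiency item, a patient with CRP of 200 mg/L and adequate ferritin and transferrin saturation is treated like one with CRP of 5 mg/L.

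Both values are measured, so the information is lost only through how the list is written.

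**Working it through.** **1. The plan's own figures (section 5.2.2).** The plan expects 255 analysable patients. It starts from 320 patients over 18 months, or 210 per year, and assumes 10% deaths and 10% lost to follow-up.

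- 320 × 0.80 = 256 and 320 × 0.9 × 0.9 = 259.2.
- 210 × 1.5 = 315, then 315 × 0.80 = 252 and 315 × 0.9 × 0.9 = 255.15.

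The figure of 255 therefore reproduces. With 67.8% regaining independence, events = 255 × (1 − 0.678) = 82.1. At 10 events per criterion that supports about 8 parameters, against 16 listed items.

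**2. What a single cut leaves uncontrolled.** For a normal variable with a share p below the cut c, a yes/no term keeps φ(c)² / [p(1 − p)] of the variance.

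| Share below 35 g/L (assumed) | Variance kept | Variance left |
|---|---|---|
| 50% | 0.637 | 0.363 |
| 30% or 70% | 0.576 | 0.424 |
| 20% or 80% | 0.490 | 0.510 |

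The share below 35 g/L and the normal shape are assumptions.

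**3. What this could do to the odds ratio: albumin alone.** This is a logistic simulation with no true haemoglobin effect and 400,000 patients per scenario. The assumed inputs are an albumin–haemoglobin correlation of 0.2 to 0.4 and an albumin odds ratio of 1.5 to 2.0 per SD. With 20% to 50% below the cut, adjusting for the flag leaves a spurious odds ratio of 1.03 to 1.14 per SD lower haemoglobin. Continuous albumin gives 0.99 to 1.01. The bias is a little larger if 80% are below the cut.

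For scale, the standard error of a log odds ratio per SD is about 1/√(255 × 0.322 × 0.678) = 0.134. Then ln 1.03 / 0.134 = 0.2 and ln 1.14 / 0.134 = 1.0, so the bias is about 0.2 to 1.0 standard errors.

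**4. Albumin and CRP acting together.** Here albumin and log CRP correlate at −0.3 or −0.5. Each has a coefficient of size 0.3 on haemoglobin and 0.4 log-odds per SD on the outcome. Between 30% and 70% fall below the albumin cut, half exceed the CRP threshold, and the true odds ratio is 1. Results are per SD higher haemoglobin.

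| Adjustment | Odds ratio | Bias removed |
|---|---|---|
| None | 0.71–0.75 | – |
| Malnutrition flag + iron-deficiency flag | 0.83–0.85 | 43–50% |
| Malnutrition flag + continuous CRP | 0.94–0.95 | 79–85% |
| Continuous albumin + continuous CRP | 0.99–1.00 | essentially all |

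With the two flags the remaining bias is −ln 0.85 / 0.134 = 1.2 to −ln 0.83 / 0.134 = 1.4 standard errors. These inputs are stronger than in step 3: the implied albumin–haemoglobin correlation is 0.3 + 0.3 × 0.3 = 0.39, or 0.3 + 0.3 × 0.5 = 0.45. Neither simulation adjusts for BMI, CIRS-G, ASA or age. Continuous terms return an odds ratio near 1 because the simulated relations are linear.

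**The case against.** **The coding is not stated.** A reader might infer that the plan commits to a yes/no albumin term. It does not. Section 4.3.e collects the albumin level and gives 35 g/L as its interpretation, and section 5.2.1 bars neither continuous albumin nor CRP. This stands. What remains is that the cut is the only definition written, and open coding can be settled after the data are seen.

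**Adjustment may not happen at all.** It requires a crude link, and then p below 0.20 for each factor. Both conditions come before any question of coding. This also stands.

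**Other candidates cover part of the ground.** BMI bears on nutrition, and CIRS-G, ASA, age and iron deficiency bear on frailty and illness. The simulated bias is therefore not that of the planned model. But none of these measures albumin, and only iron deficiency uses CRP, as a threshold.

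**The inflammation argument has a timing limit.** Section 1.1 says "Finally, there is a degree of acute inflammatory anaemia secondary to surgery". CRP taken before the operation cannot measure that. It can measure only baseline inflammation. It does precede the day 5 haemoglobin, which suits a confounder.

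**Dehydration does not decide the matter.** Section 2.1.2 says dehydration shifts admission haemoglobin. A reader might extend this to albumin crossing the cut, but a continuous albumin term would carry the same error.

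**Parameters are scarce.** With room for about 8, a case for forcing albumin and CRP into every adjusted model would have to show why they outrank, for example, age or cognition. The documents give no such reason.

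**Conclusion.** The point holds as a gap in specification with a better method at hand. Malnutrition has one written definition, a cut at 35 g/L, and admission CRP is not a candidate in its own right. If that definition is carried into the model, 36% to 51% of albumin's variance is left unadjusted by that term. This assumes near-normal albumin and 20% to 80% of patients below the cut.

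The bias is towards a harmful-looking effect of low haemoglobin, provided that low albumin or high CRP goes with both lower haemoglobin and worse recovery. It is probably modest, because other listed factors would absorb some of it. That is a judgement: the illustrative values of 0.2 to 1.4 standard errors rest wholly on assumed correlations and effects.

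A reader might infer that the planned association is materially inflated. The documents do not support that, since they give no correlation, no effect size and no final covariate set.

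**What to change.** In sections 2.1.2 and 5.2.1:

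- State that admission albumin is analysed as a continuous variable in g/L, in place of the malnutrition flag.
- Add log-transformed admission CRP to the list of candidate confounders, under the same entry rule as the others.
- Keep the class below 35 g/L for describing the population only.
- Say that admission CRP represents pre-operative inflammation, so that inflammation caused by surgery remains unadjusted.

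The cost is wording. No new sampling is needed, since both values are in the admission panel. Continuous albumin, entered linearly, uses the same one parameter as the flag. CRP uses at most one more of the roughly 8. Section 5.2.4 rules out imputation, so patients without a CRP value would drop out of any model that retains it; the report should give their number.

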4.3. DESCRIPTION DETAILED OF THE EVALUATION AND THE DATA COLLECTED

a. On patient autonomy:

- **Activities of Daily Living (ADL)** (21): Measured at inclusion (information relating to the week preceding the procedure) (questioning of patient, family, nursing home staff), on day 5 post-op (or on discharge from hospital if discharged before day 5) (*in hospital*), 1 month, 3 months and 6 months post-op (*telephone call*).

Validated scale for assessing independence in simple activities of daily living: hygiene, dressing, mobility, going to the toilet, continence, eating. Each item is coded as follows:

1: done independently

0.5: done partially or with assistance

0: not done

Scale ranging from 0 to 6, with a high score indicating a more independent patient.

- Lawton's 4-item **Instrumental Activities of Daily Living (IADL)** (22): Measured at inclusion (information relating to the week preceding the intervention) (questioning of patient, family, nursing home staff), at 1 month, 3 months and 6 months post-operatively (*telephone call*).

Validated scale for assessing patient autonomy in so-called "instrumental" activities of daily living: managing finances, preparing medication, using the telephone, using transport. Each item is coded as follows:

1 : done alone

0.5: does partially or with assistance

0: does not do

The score ranges from 0 to 8. A high score indicates that the patient is independent. This score can only be interpreted for subjects living at home.

- **Cumulative Ambulation Score** (23): Measured at inclusion (information relating to the week preceding the procedure), from D1 to D3 post-operative, on D5 post-operative (or on discharge if before D5) (*in-hospital*), and at 1 month, 3 months and 6 months (*telephone call*)

Validated score predictive of mortality, morbidity and rehabilitation. Three areas (transfer from lying to sitting, transfer from sitting to standing, walking with appropriate aids) are assessed from 0 (unable despite the help of two people) to 2 (able to do independently). The scores are cumulative over the first 3 days post-operatively and give a score of 0 to 18. A cumulative score greater than 10 corresponds to a 99% probability that the patient will be alive at one month, 93% that they will have returned home, and 94% that they will not have had any major post-operative complications.

b. On the patient's physical performance:

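### Falls and fractures that follow the reference haemoglobin are listed as confounders with no timing rule, so the adjusted models can be over-adjusted; pre-fracture ADL is collected but never named as a covariate

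*Combined protocol and SAP*

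**What the plan says.** The exposure in section 2.1.2 is haemoglobin on day 5, or at the end of hospitalisation for patients transfused post-operatively. The outcome is a fall of at least one ADL point between the pre-fracture state and month 6. The same section lists 16 confounder items. Two include information from after the exposure: "Recurrence of falls at 1, 3 and 6 months post-op" and "Severe fractures before and after inclusion". A third, "Other falls during the year", does not say which year is meant.

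Section 5.2.1 starts with an unadjusted logistic model. Only if that shows a link does a multivariate model follow, to establish that the link is independent. For that model, "all potential confounding factors will be tested in a univariate analysis", and "Factors associated with a p value <0.20 will be retained in the multivariate model". The analyses of loss at day 5, month 1 and month 3 "will be performed using the same method as for the primary endpoint".

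Other listed items are measured more than once, or at no fixed time: living arrangements (inclusion, months 1, 3 and 6), medications (inclusion, end of stay, month 6) and higher-function disorders (inclusion and hospital stay), all in section 4.3 e; and transfusion, which section 4.4 allows to be post-hospital.

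Pre-fracture ADL is collected at D0 (section 4.1, "information relating to the week preceding the intervention"). It is not on the confounder list, and no section names it as a covariate.

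**The concern.** A confounder has to precede the exposure or share a cause with it. A fall at month 3 cannot have influenced haemoglobin on day 5. It may be a consequence of anaemia, in which case adjusting for it takes out part of the association under study. It may also be a consequence of lost independence, in which case adjusting for it distorts the comparison. The time order is plainest in the secondary models: read literally, a fall at month 6 is a candidate covariate for ADL loss at day 5.

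This matters because the multivariate model is the step on which the claim of an independent link rests.

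The secondary issue is baseline function. Section 1.1 names low previous independence among the strongest risk factors, and describes a cited cohort that adjusted for pre-fracture function. If pre-fracture ADL is related to both haemoglobin and loss, a model without it keeps residual confounding. Defining the outcome as a change does not settle this. The ADL is a "Scale ranging from 0 to 6, with a high score indicating a more independent patient", scored in half points, so a patient starting at 0 or 0.5 cannot lose a point. The documents do not say how many such patients to expect.

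**Working it through.** **The plan's own figures (section 5.2.2).** With 10% mortality and 10% loss to follow-up, 320 × (1 − 0.10 − 0.10) = 256, or 320 × 0.9 × 0.9 = 259. The stated 255 is consistent with these. Expected events are 255 × (1 − 0.678) = 82, which at 10 events per criterion allows about 8 terms. If half of patients lose independence (section 1.1 reports nearly half at one year), there are 128 events and about 12 terms.

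**Over-adjustment: inputs.** From the documents: n = 255; anaemia 65% (a cited study's share below 10 g/dL); loss 32.2% (1 − 0.678, a 12-month figure from previously autonomous, home-living patients). Assumed, because the documents give nothing: fall rate 25%; anaemia–fall odds ratio (OR) 1.25, 1.5, 2 or 2.5; fall–loss OR 1.5, 2 or 3; direct anaemia–loss OR 1.3, 1.5 or 2.0. That makes 36 scenarios, computed exactly with intercepts solved to match the margins.

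Share removed = 1 − ln(direct OR) / ln(total OR), where the direct OR is the one with falls in the model.

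**One scenario in full** (anaemia–fall 1.5, fall–loss 2, direct 1.5):

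- Fall risk: 0.276 if anaemic, 0.202 if not (0.65 × 0.276 + 0.35 × 0.202 = 0.25).
- Loss odds without a fall: 0.300 if not anaemic, 0.300 × 1.5 = 0.450 if anaemic; doubled with a fall.
- Loss risk, not anaemic: 0.202 × 0.375 + 0.798 × 0.231 = 0.260.
- Loss risk, anaemic: 0.276 × 0.474 + 0.724 × 0.310 = 0.355.
- Total OR: (0.3554/0.6446) / (0.2600/0.7400) = 1.569.
- Share removed: 1 − 0.4055/0.4507 = 10%.
- Standard error (SE) of the log OR: √[1/(165.75 × 0.3554 × 0.6446) + 1/(89.25 × 0.2600 × 0.7400)] = 0.291. Shift: (0.4507 − 0.4055)/0.291 = 0.16 SE.
- Chance that the multivariate model is run (two-sided p<0.05): z = 0.4507/0.291 = 1.55, giving 34%.

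**All 36 scenarios, share of the log OR removed:**

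| Fall rate | Loss | Median | Quartiles | Range |
|---|---|---|---|---|
| 25% | 32.2% | 11.0% | 6.3–18.3% | 1.7–39.3% |
| 15% | 32.2% | 7.8% | 4.3–13.0% | 1.1–30.3% |
| 35% | 32.2% | 13.1% | 7.5–21.5% | 2.2–44.1% |
| 25% | 50% | 10.2% | 5.7–16.8% | 1.1–36.7% |

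At a 25% fall rate the shift is 0.17 SE at the median and 0.59 SE at most; at 35% the maximum is 0.71 SE. The multivariate model is run in 16% to 79% of trials. Falls pass p<0.20 in 54% or more, or 46% or more at a 15% fall rate. If anaemia and falls are unrelated, nothing is removed.

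**Baseline ADL.** Assumed: low ADL in 40%; anaemia–low-ADL OR 1.25, 1.5 or 2; low-ADL–loss OR 0.33, 0.5, 2 or 3; true anaemia OR 1.0. Worked extreme (2 and 3): low ADL in 0.4562 of anaemic and 0.2955 of other patients; loss risks 0.3355 and 0.2968; apparent OR (0.3355/0.6645) / (0.2968/0.7032) = 1.20. Over the 12 scenarios the apparent OR runs from 0.85 to 1.20. With one assumed proxy of 80% sensitivity and specificity it runs from 0.90 to 1.13. In these scenarios the multivariate model would be run only about 5% to 10% of the time.

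**The case against.** **The effect may be small.** The documents give no anaemia–fall or fall–loss figure, the median shift is 0.17 SE, and it is zero if the two are unrelated. This stands. The case for change rests on time order and on the negligible cost, not on a demonstrated large bias.

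**Using the same method need not mean using the same covariate values.** An analyst might sensibly leave month-6 falls out of a day-5 model, and use inclusion values where an item is measured repeatedly. That is a fair reading, but nothing in the text requires it. The month 1, 3 and 6 falls are listed by date, so for the primary model no such reading removes them.

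**Pre-fracture ADL is unnamed, not excluded.** The words on potential confounders are wide enough to take it in, and section 1.1 points to it. On the odds ratios assumed above it would pass p<0.20 in 87% to 99.6% of cases. This largely stands, and is why the point is secondary. A reader might infer that the plan leaves baseline function out of its adjusted analysis; the documents do not support that. Living arrangements, CIRS-G, ASA and cognition are also listed, as partial proxies.

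**Adjusting a change for its own baseline is debated in non-randomised data**, because of measurement error and regression to the mean. This stands, and the fix allows for it.

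**Conclusion.** The timing point holds with high confidence: as written, sections 2.1.2 and 5.2.1 admit possible mediators and, in the secondary models, covariates later than the outcome. Under the assumed effects the loss is typically about a tenth of the log odds ratio, rising to 39% at a 25% fall rate, and none without an anaemia–fall link. It should be corrected before analysis, but it is not fatal.

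Four stronger readings go beyond the documents:

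- That the primary result as a whole is over-adjusted. The unadjusted model contains no later covariate. Over-adjustment arises only in the conditional multivariate step and in the secondary models that copy it.
- That the baseline problem is confined to that same step. It is not: the unadjusted model, which decides whether the multivariate model is run, is also open to confounding by pre-fracture ADL.
- That the 16% to 79% chance of running the multivariate model applies to both issues. It belongs to the over-adjustment scenarios; the baseline scenarios, at a true OR of 1.0, give about 5% to 10%.
- That the net bias has a known direction. Over-adjustment pulls towards the null in these scenarios, baseline confounding can go either way, and the documents cannot sign the sum.

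Confidence on pre-fracture ADL is lower, and the recommendation there is to name it.

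**What to change.** Amend sections 2.1.2 and 5.2.1 before analysis:

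1. Restrict covariates to values fixed before the reference haemoglobin and before the outcome of the model concerned. Use inclusion values for living environment, medications and cognition; transfusions before the reference haemoglobin; and fractures before inclusion.
2. State that the item on falls during the year means falls before the fracture, if these were recorded. The timeline in section 4.1 shows only fractures at D0, and the data-collection appendix is not in the available text. If they were not recorded, drop the item.
3. Remove falls at months 1, 3 and 6 and fractures after inclusion from the candidates. Report them descriptively or as outcomes.
4. Name pre-fracture ADL and keep it, as one term, in the adjusted ADL models whatever its p value. Report the same models without it as well.

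The cost is wording. No new data are needed, and no patient is lost, because section 5.2.5 already requires the preoperative autonomy record. Pre-fracture ADL uses one of about 8 terms; step 3 frees between one and four candidates, depending on how falls and fractures would have been coded. Two things remain unsolved: baseline confounding in the unadjusted model, and a candidate list still longer than about 8 terms.
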